- A problem/event experienced by a subject that is life threatening and possibly, probably or definitely related to the study procedures, should be reported within 7 calendar days (1 week) of investigator's receipt of information:
 - All other internal serious and unanticipated problems/events that are possibly, probably or definitely related to study procedures, must be reported within 14 calendar days (2 weeks) of investigator's receipt of information.
 - An unanticipated problem is any event that affects the rights, safety, or welfare of subjects or others. The event could be physical, such as an adverse experience. The event also could involve social harm or risk (i.e., a breach in confidentiality or harm to a subject's reputation) or psychological or legal harm or risk. Examples of unanticipated problems include, but are not limited to, breach of confidentiality, protocol violations and deviations, and complaints about the research procedures or treatment by key personnel on the research study.
 - A serious unanticipated problem is any event that results in significant harm to or increased risk for the subject or others.
 - If there is insufficient information to determine if the event is associated, it should be reported.
- 13.6 Markey Data and Safety Monitoring System (DSMS): The Markey Cancer of the University of Kentucky has established a system for following clinical oncology trials. This mechanism will be used as the Plan for monitoring this trial.
 - 13.6.1 Components: Quality Assurance Committee (QAC); Protocol Review Committee (PRC).
 - 13.6.2 Quality Assurance Committee (QAC): The QAC provides oversight and monitoring of clinical trials. The Committee is responsible for reviewing data to identify patient safety and protocol compliance issues. The Markey Protocol Review Committee (PRC) assigns studies a QAC timeline based on the phase, origination of the study and known safety issues.
 - 13.6.3 QAC Membership: The members of the QAC consists of Medical Oncologists, a Pharmacist, a Nurse Manager, a Certified Clinical Research Professional and a

Reporter. These members are selected based on their experience, reputation for objectivity and knowledge of clinical trial methodology. All member view themselves as representing the interest of the study patients and not that of the institution.

13.6.4 QAC Review: At each meeting, the following study data is reviewed by the QAC: treatment issues, serous adverse events (SAE's) per FDA's definition, dose levels, dose modifications, and responses as applicable.

The QAC reviews protocols to assure the following:

- · progress of the trial and safety of participants,
- compliance with requirements regarding the reporting of severe adverse events,
- that any action resulting in a temporary of permanent suspension of this clinical trial is reported to the responsible program director, and
- data accuracy and protocol compliance.

13.6.4.2 Study Suspension: The Markey Quality Assurance Committee, the responsible disease-specific CCART and/or the UK/VA IRB are empowered to immediately suspend accrual to a study for any of the following: Failure to comply with AE/SAE reporting requirements, poor study enrollment, protocol violations, or issues related to patient safety.

13.7 Reporting by supporter to investigator concerning Adverse event updates/IND safety reports:

Celgene shall notify the Investigator via an IND Safety Report of the following information:

- Any AE associated with the use of study drug in this study or in other studies that is both serious and unexpected.
- Any finding from tests in laboratory animals that suggests a significant risk for human subjects including reports of mutagenicity, teratogenicity, or carcinogenicity.

 The Investigator shall notify his/her IRB/EC promptly of these new serious and unexpected

AE(s) or significant risks to subjects.

The Investigator (sponsor) must keep copies of all AE information, including correspondence with Celgene and the IRB/EC, on file (see Section 13.8 for records retention information).

13.8 Study Records Requirements: The Investigator (sponsor) will ensure that all records and documents pertaining to the conduct of the study and the distribution of the study drug, that is copies of CRFs and source documents (original documents, data, and records [e.g., hospital records; clinical and office charts; laboratory notes; memoranda; subject's diaries or evaluation checklists; pharmacy dispensing records; recorded data from automated instruments; copies or transcriptions certified after verification as being accurate copies; microfiches; photographic negatives, microfilm, or magnetic media; x-rays; subject files; and records kept at the pharmacy, at the laboratories, and at medico-technical departments involved in the clinical study; documents regarding subject treatment and study drug accountability; original signed informed consents, etc.]) be retained by the Investigator for as long as needed to comply with national and international regulations (generally 2 years after discontinuing clinical development or after the

last marketing approval). The Investigator agrees to adhere to the document/records retention procedures by signing the protocol.

- 13.9 Subject confidentiality and supporter access to information: The Investigator and the supporter, Celgene, affirm the subject's right to protection against invasion of privacy. In compliance with United States federal regulations, Celgene requires the Investigator to permit Celgene's representatives and, when necessary, representatives of the FDA or other regulatory authorities to review and/or copy any medical records relevant to the study in accordance with local laws. Should direct access to medical records require a waiver or authorization separate from the subject's statement of informed consent, it is the responsibility of the Investigator to obtain such permission in writing from the appropriate individual.
- 14.0 Protocol amendments: Any amendment to this protocol must be agreed to by the Principal Investigator (sponsor) and reviewed by Celgene. Written verification of IRB/EC approval will be obtained before any amendment, which affects subject safety or efficacy, is implemented.

15.0 References:

- 1. **[name] KB, [name] C, Williams K** 2002 Phase II trial of thalidomide for therapy of radioiodine-unresponsive papillary and follicular thyroid carcinomas and medullary thyroid carcinomas: preliminary results. Cancer Invest 21:Suppl 1, 38-9

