1.7.2.3 The following studies are obtained once every 28-day cycle while on therapy

Toxicity Monitoring:

Obtain CBC with differential/platelet count (weekly for the first 2 cycles); and physical examination monthly. Biochemistry panels are obtained at visits for cycles 4, 8, and 12.

Pregnancy Counseling and Testing:

Pregnancy tests for females of childbearing potential. A Female of Childbearing Potential (FCBP) is a sexually mature female who: 1) has not undergone a hysterectomy or bilateral oophorectomy; or 2) has not been naturally postmenopausal for at least 24 consecutive months (i.e., has had menses at any time in the preceding 24 consecutive months).

Pregnancy tests must occur 10-14 days and again within 24 hours prior to initiation of lenalidomide. FCBP with regular or no menstruation must have a pregnancy test weekly for the first 4 weeks and then every 28 days while on therapy (including breaks in therapy); at discontinuation of lenalidomide and at 30 Days +/- 2 days post the last dose of lenalidomide. Females with irregular menstruation must have a pregnancy test weekly for the first 4 weeks and then every 14 days while on therapy (including breaks in therapy), at discontinuation of lenalidomide and at Day 14 and Day 28 post the last dose of lenalidomide (see Appendix F: Risks of Fetal Exposure, Pregnancy Testing Guidelines and Acceptable Birth Control Methods).

All patients must be counseled about pregnancy precautions, risks of fetal exposure and other risks. The counseling must be done at screening and on Day 1 of each cycle including Cycle 1 (or at a minimum of every 28 days). The Appendix G: Education and Counseling Checklist must be completed by a trained counselor.

1.7.3 Studies at Termination of Protocol: The following studies are obtained when terminating the protocol due to either disease progression, severe toxicity or at the conclusion of one year of REVLIMID® treatment:

Tumor Assessment:

Tumor markers: Thyroglobulin Panel (TG & anti-TG Ab), TSH, free T4.
CONFIDENTIAL

Angiogenic Markers: serum samples for VEGF-A, sVEGFR-1, sVEGFR-2, and TSP-1.

Radiological Studies: CT (without contrast for lung; otherwise with contrast) of evaluable disease.

Toxicity Monitoring: CBC with differential/platelet count, biochemistry panel, and physical examination. Pregnancy test should be repeated 30 days after the last dose of study drug.

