1.7.4 Studies during the "Extended Therapy" phase: The following studies are obtained after the one-year protocol has concluded and the patient is maintaining a clinical response to REVLIMID® therapy and elects to continue to receive this drug. Note that these studies are performed as "standard-of-care" assessments that are appropriate for oncologic follow-up:

Tumor Assessment (obtained at physician visits every 3 months): Tumor markers: Thyroglobulin Panel (TG & anti-TG Ab), TSH, free T4. Angiogenic Markers: Not done. Radiological Studies: CT (without contrast for lung; otherwise with contrast) of evaluable disease.

Toxicity Monitoring (obtained every month while taking REVLIMID®): CBC with differential/platelet count every 4 weeks.

FCBP with regular or no menstruation must have a pregnancy test every 28 days while on therapy (including breaks in therapy); at discontinuation of lenalidomide and at 30 Days +/- 2 days post the last dose of lenalidomide. Females with irregular menstruation must have a pregnar every 14 days while on therapy (including breaks in therapy), at discontinuation of lenalidomide and at Day 14 and Day 28 post the last dose of lenalidomide (see Appendix F: Risks of Fetal Exposure, Pregnancy Testing Guidelines and Acceptable Birth Control Methods).

Additional standard assessments (obtained at physician visits every 3 months): biochemistry panel and physical examination.

- Outpatient Visits: Patients will report to the University of Kentucky Clinical Research Organization (UKCRO) for outpatient evaluations by the principal investigator and UKCRO nursing staff at: time of initial enrollment, at the start of every 28 day cycle and for a final visit.
 - 1.8.1 Study Duration: Each patient will continue on study for 12 28-day cycles or until there is evidence of disease progression (or patient withdraws from study), whichever is sooner.
 - 1.8.2 Final Visit: Should any patient terminate participation at any time, either out of choice, disease progression, or significant toxicity, there will be a final outpatient visit. Toxicity assessment will be done approximately 30 days after last dose of study drug.

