- 4.2 Assess any differences in the anti-tumor activity of REVLIMID® between histiotypes of papillary (typical, tall cell, columnar cell, oxyphilic/Hürthle cell) and follicular (typical, oxyphilic/Hürthle cell, insular) thyroid carcinomas.
- 4.3 Evaluate treatment toxicities and duration of toxic effects.
- 4.4 Evaluate markers of tumor angiogenesis: serum levels of vascular endothelial growth factor (VEGF-A), soluble VEGF receptors (sVEGF-1 & sVEGF-2), and thrombospondin-1, to determine if they change in response to treatment and correlate with primary objectives and disease status.

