- 5.2.4.3 Labeling: REVLIMID® investigational supplies that are dispensed to the patients by the investigational pharmacy are supplied in individual bottles of capsules. Each bottle that is dispensed by the investigational pharmacy will identify the contents as study medication. It will also bear Celgene's name and address, quantity contained and the standard caution statement as follows: Caution: New Drug Limited by Federal Law to investigational use. For appropriate drug accountability, it is recommended that each bottle be marked with the institutional or Celgene protocol number (RV-THYR-PI-057) upon receipt. Additional labels must not cover the Celgene label.
- 5.2.4.4 Storage: The Study Pharmacist at the investigational pharmacy will store all investigational study drugs in an appropriately secure area to prevent unauthorized access. The study drug will be stored at room temperature away from direct sunlight and protected from excessive temperature ranges.
- 5.2.4.5 Unused Study Drug Supplies: Patients that have been provided REVLIMID® through the investigational pharmacy will be instructed to return emp⁺ bottles or unused capsules. Celgene will instruct the Investigator on the return destruction of unused study drug. If any study drug is lost or damaged, its disposition should be documented in the source documents. Study drug supplies will be retained by the Study Pharmacist, pending instructions for disposition by Celgene.
- 5.2.4.6 Record of Administration: Accurate records will be kept of all study drug administration (including dispensing and dosing).
- 5.2.5 Dose Modification or Interruption: Subjects will be evaluated for Adverse Events (AEs) at each visit, using the NCI Common Terminology Criteria for Adverse Events, version 3.0 (CTC; appendix C) as the guide for the grading of severity. Refer to Table 2: Revlimid® Dose Reduction Steps For Dose Modification and Table 3: Dose Modification for Revlimid® for instructions on dose modifications. Subjects who cannot tolerate a dosage of at least 5 mg daily will be discontinued from the treatment phase of this study (unless the subject has achieved a plateau phase of response to study therapy; such subjects will continue to adhere to the schedule of assessments followed during the treatment phase of the study, even though the study drug has been discontinued, until disease progression).

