Once the REVLIMID® dose is initiated at 25 mg/day, taken in the morning or approximately the same time each day, it will be maintained at this dose for the duration of the study unless dose modification is necessary due to toxicity. If a dose of CONFIDENTIAL

- lenalidomide is missed, it should be taken as soon as possible on the same day. If it is missed for the entire day, it should not be made up.

Patients who take more than the prescribed dose of lenalidomide should be instructed to seek emergency medical care if needed and contact study staff immediately.

Table 2

Dose adjustments will be made for toxicity as needed, until a stable tolerable dose is achieved or a dose of at least 5 mg/day is unable to be tolerated, resulting in discontinuation of REVLIMID®. If REVLIMID® is held, toxicity should be assessed weekly and if therapy cannot be resumed within 4 weeks of holding therapy, the patient will be removed from the study.

Table 2: Revlimic	® Dose Reduction Steps
Starting Dose	25 mg daily (28-day cycles)
Dose Level -1	20 mg daily every 28 days
Dose Level -2	15 mg daily every 28 days
Dose Level -3	10 mg daily every 28 days
Dose Level -4	5 mg daily every 28 days

Table 3

"able 3"		
1	REVLIMID® DOSE MODIE	u .
TOXICITY	GRADE	Dose Level Change
Rash / Desquamation	Rash: II	Hold until resolution to ≤ grade I; resume a' one level dose reduction. Further dose reductions are permitted to a minimum of 5 mg
·	Rash: III	Hold until resolution to ≤ grade I; resume with 2 dose level reductions or a minimum of 5 mg. If grade III rash recurs discontinue therapy.
,	Rash: IV or any grade desquamating (blistering) rash or erythema multiforme ≥ grade III	Discontinue drug
Sinus bradycardia, atrial fibrillation or other cardiac arrhythmias	п	Hold until resolution to ≤ grade I, resume at one dose level reduction. Additional dose reductions are permitted to a minimum of 5 mg.
	Ш	Discontinue drug
	īV	Discontinue drug
Neutropenia	III or IV	Hold, CBC weekly until resolution to ≤ grade II,; resume at one dose level reduction. Additional dose reductions are permitted to a minimum of 5 mg.
Thrombocytopenia	III or IV	Hold, CBC weekly until resolution to ≤ grad- 2,; resume with one dose level reduction, additional dose reductions are permitted to a minimum of 5 mg.
Venous thrombosis or		Hold drug & anticoagulate, restart at one
embolism	ш	dose level reduction
	ïV	Discontinue drug & anticoagulate

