Allergic reaction or Hypersensitivity	II	Hold until resolution to ≤ grade I; resume at one dose level reduction. Additional dose reductions are permitted to a minimum of 5 mg.
_	ш	Hold until resolution to \leq grade I; resume at two dose level reductions to a minimum of 5 mg. If grade III recurs, discontinue therapy
	IV	Discontinue drug
Other non-hematological toxicity assessed as Revlimid-related	ш	Hold until resolution to ≤ grade II; resume at one level dose reduction. Additional dose reductions are permitted to a minimum of 5 mg.
	IV	Discontinue drug

G-CSF is not permitted during this study unless needed to treat severe neutropenia or neutropenic fever. Otherwise, neutropenia should be managed as outlined in the table above. Filgrastim is not provided by this study. Subjects should receive full supportive care, including transfusions of blood and blood products, antibiotics, and antiemetics when appropriate. The use of radiation therapy &/or surgery to a pre-existing metastatic bone lesion may be permitted while continuing on this protocol as long as it is not an evaluable site of disease and does not represent disease progression

In the event that the daily dose schedule of Revlimid is causing repeat hematologic toxicity that needs time to resolve, consideration may be given to modify the schedule from daily every 28 days to daily for 21 days followed by 7 days of rest each month. This modification must be discussed and approved by the Principal Investigator of the study.

5.2.6 Extended Therapy phase: At one year after starting this protocol, those patients that are maintaining tumor response to REVLIMID® treatment and wish to continue these treatments will enter into the "Extended Therapy" phase. These patients may elect to continue with extended drug therapy in 28-day cycles through the RevAssist program see Appendix 1, with treatment response and routine tumor assessment every three months. This phase will continue, indefinitely, as long as the patient tolerates the medication and continues to manifest a tumor response. This phase may be terminated by Celgene Corporation, the principle investigator, or the patient at any time.

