- 7.0 Evaluation During Study: Please refer to Table 1: Schedule of Study Assessments
 Physical examination and history (clinic visit): monthly for the first 2 28-day cycles, then every 2
 28-day cycles while on the study.
 - 7.1 Tumor Assessment: The following studies are obtained every 2 28-day cycles while on therapy:
 - 7.1.1 Tumor markers: thyroglobulin panel, TSH, free T4.
 - 7.1.2 Radiological Studies: CT (without contrast for lung metastases; otherwise with contrast) &/or MRI of evaluable disease. Radiological studies will be financed by the research study at 28-day cycles 2, 6, & 10 (if the patient remains on the protocol for that length of time). Baseline radiological studies and those at the intervals of 28-day cycles 4, 8, &-12 will be financed by the patient &/or 3rd party payers, representing appropriate intervals of assessing progressive metastatic tumors for usual clinical standards of care.
 - 7.2 Angiogenic Markers: The following studies are obtained monthly for the first 2 28-day cycles, then every 2 28-day cycles while on therapy:
 - 7.2.1 Proangiogenic cytokine: VEGF-A.
 - 7.2.2 Antiangiogenic factors: sVEGFR-1, sVEGFR-2, and TSP-1.

7.3 Toxicity Monitoring:

- 7.3.1 Hematological: Weekly: CBC with differential and platelet count for the first 2 cycles then monthly. Obtain biochemistry panel at cycles 4, 8 and 12.
- 7.3.2 Pregnancy prevention (Pregnancy tests must occur within 10 14 days and again within 24 hours prior to initiation of lenalidomide. FCBP with regular or no menstruation must have a pregnancy test weekly for the first 4 weeks and then every 28 days while on therapy (including breaks in therapy); at discontinuation of lenalidomide and at 30 Days +/- 2 days post the last dose of lenalidomide. Females with irregular menstruation must have a pregnancy test weekly for the first 4 weeks and then every 14 days while on therapy (including breaks in therapy), at discontinuation of lenalidomide and at Day 14 and Day 28 post the last dose of lenalidomide (see Appendix F: Risks of Fetal Exposure, Pregnancy Testing Guidelines and Acceptable Birth Control Methods).
- 8.0 Evaluations at Termination of Protocol: The following studies are obtained when terminating the protocol due to either disease progression, severe toxicity or at the conclusion of one year of REVLIMID® treatment:

8.1 Tumor Assessment:

- 8.1.1 Tumor markers: thyroglobulin panel, TSH, free T4.

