- 9.1.5 Progressive disease (PD): Less than a 50% reduction in the rate of progression (see 9.1.3), an increase of >20% in the size of target lesions, or the appearance of new metastatic lesions.

Figure 4. Overall responses for all possible combinations of tumor responses in target and non-target lesions with or without the appearance of new lesions* (Adapted from Therasse P, Arbuck SG, Eisenhauer EA, Wanders J, Kaplan RS, Rubinstein L, Verweij J, Van Glabbeke M, van Oosterom AT, Christian MC, Gwyther SG 2000 New guidelines to evaluate the response to treatment in solid tumors. European Organization for Research and Treatment of Cancer, National Cancer Institute of the United States, National Cancer Institute of Canada. J Natl Cancer Inst 92:205-16)

Target lesions	Non-target lesions	New lesions	Overall response
CR.	CR	No	CR
CR.	Incomplete response/MR/SD	No	PR
PR.	Non-PD	No	PR.
MR	Non-PD	No	MR
SD	Non-PD	No	SD
PD	Any	Yes or no	PD
	PD	Yes or no	PD
Any Any	Any	Yes	PD + 1.1a disease

^{*}CR= complete response; PR= partial response; MR= minor response; SD= stable disease; and PD= progressive disease.

9.2 Toxicity Assessment: This will be performed at intervals defined in section 7.0 using criteria defined in appendices A, B, & C.

10.0 Criteria for Discontinuing Therapy:

- 10.1 Progressive Disease is an indication to discontinue therapy.
- Adverse event(s) that, in the judgment of the Investigator, may cause severe or permanent harm or which rule out continuation of the study drug.
- 10.3 Non-compliance by the patient with protocol requirements.
- 10.4 Patient desire to discontinue therapy.
- 10.5 Evidence of pregnancy.

- 10.6 ... Withdrawal of consent.
- 10.7 Lost to follow-up.
- 10.8 Death

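### On-treatment chemistry is scheduled only at cycles 4, 8 and 12, so silent grade III/IV renal, hepatic or electrolyte toxicity may be found late, with no scheduled panel for the first 84 to 112 days.

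*Combined protocol and SAP*

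**What the plan says.** The on-treatment schedule is given twice in the text, and the two places agree. Section 7.3.1 reads "Obtain biochemistry panel at cycles 4, 8 and 12"; section 1.7.2.3 reads "Biochemistry panels are obtained at visits for cycles 4, 8, and 12". One Table 1 row is marked only at screening and cycles 4, 8 and 12, which fits, although its label is illegible in the copy read.

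Chemistry is otherwise scheduled before treatment (sections 1.7.1, 6.1 and 6.4.2), at termination (1.7.3) and in the extension, where 1.7.4 has "Additional standard assessments (obtained at physician visits every 3 months): biochemistry panel and physical examination".

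Three other provisions depend on this schedule:

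- Section 5.2.5 states "Subjects will be evaluated for Adverse Events (AEs) at each visit". Section 9.2 says of toxicity assessment "This will be performed at intervals defined in section 7.0".
- The last row of Table 3, "Other non-hematological toxicity assessed as Revlimid-related", requires a hold and dose reduction at grade III and discontinuation at grade IV.
- Objective 4.3 is "Evaluate treatment toxicities and duration of toxic effects".

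**The concern.** Table 3 presumes that a grade is available. A rise in creatinine or transaminases, or an electrolyte disturbance, can reach grade III or IV without symptoms and can then be graded only from a blood chemistry. In cycles 1 to 3 the scheduled tests are CBC, thyroid markers, angiogenic markers, pregnancy tests and physical examination, and none of these supplies the grade.

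The plan is strict once a problem is known: "If REVLIMID® is held, toxicity should be assessed weekly". The measurement that would trigger the hold is much less frequent.

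Two things are at stake. The first is safety. Entry allows creatinine up to 2 mg/dL, and transaminases up to 5 times the upper limit with liver metastases. Every patient starts at 25 mg daily, which section 3.5 gives as the maximum tolerated dose. The same section reports that about two thirds of a dose leaves unchanged in the urine, so an undetected fall in renal function would also bear on drug exposure. The second is ascertainment. A laboratory event that begins and resolves between panels is never recorded, and the onset of any other is known only to within the gap. Both weaken objective 4.3.

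**Working it through.** The plan states no figure for detection delay, so there is nothing to reproduce. The check is schedule arithmetic.

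**Inputs.** Cycle length is 28 days and treatment lasts 12 cycles (section 1.8.1), so 12 × 28 = 336 days. Visits open each cycle (section 1.8). Panels are at cycles 4, 8 and 12 (1.7.2.3, 7.3.1). The starting dose is 25 mg daily (5.2.4).

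**Time to the first on-drug panel.** The start of cycle k is 28 × (k − 1) days after the first dose, and its end is 28 × k days.

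- Start of cycle 4: 28 × 3 = 84 days, or 84/336 = 25% of treatment.
- End of cycle 4: 28 × 4 = 112 days, or 112/336 = 33%.
- Dose taken by then, without holds or reductions: 84 × 25 = 2,100 mg to 112 × 25 = 2,800 mg.

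**Later gaps.** Cycle 4 to 8 and cycle 8 to 12: 4 × 28 = 112 days, or 16 weeks. The extension's 3-monthly interval is 365.25/4 ≈ 91 days, or about 13 weeks.

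**Mean delay.** If onset is uniform within a gap (an assumption), the mean wait for the next scheduled panel is half the gap.

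| Window | Gap (days) | Mean delay (days) |
|---|---|---|
| First, start-of-cycle reading | 84 | 42 |
| First, end-of-cycle reading | 112 | 56 |
| Later windows | 112 | 56 |
| Panel every cycle | 28 | 14 |

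**Visits without chemistry.** Table 1 and 1.7.2.3 give 12 cycle visits, so 12 − 3 = 9 have no panel. Section 7.0's own text gives visits at cycles 1, 2, 4, 6, 8, 10 and 12, so 7 − 3 = 4 have none. If visits open the cycle, the cycle 1 visit precedes meaningful exposure, and the counts become 8 of 11 and 3 of 6.

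The documents give no rate for silent grade III/IV chemistry toxicity, so no expected number of missed events can be calculated.

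**The case against.** The strongest reply is that this is a consistent, risk-based choice. Section 3.5 names myelosuppression as the dose-limiting toxicity, and the CBC is weekly for two cycles and then monthly. The direct evidence on chemistry is mostly reassuring: section 3.5 reports no effect on renal function in single-dose studies and SGPT rises below twice the upper limit in an 8-day trial, and section 3.4 reports no biochemical toxicity in the solid-tumour phase I study. Renal failure appears only in a list compiled regardless of causality. That evidence limits the weight of the concern but does not close the gap. It comes from single doses, 8 days of dosing and 19 phase I patients, which says little about three months at 25 mg in this population.

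Other safeguards exist. Exclusion 7 lets the investigator refuse patients whose laboratory abnormalities pose unacceptable risk, but it works only at entry. Adverse events are reviewed at visits, section 10.2 allows stopping on judgement, and nothing bars unscheduled tests. These cover symptomatic toxicity; for silent events, optional testing gives neither uniform protection nor uniform recording. The termination panel tests patients who are coming off drug.

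Two points on the figures stand. Start-of-cycle visits are the better reading, and then the first gap of 84 days is slightly shorter than the extension's 91; only the later gaps are longer. The cumulative dose describes exposure and is not evidence of harm, since section 3.5 reports no accumulation with repeated dosing.

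**Conclusion.** The concern holds. No chemistry is scheduled for the first 84 days on drug (112 on the end-of-cycle reading), and the later gaps are 112 days, longer than in the standard-of-care extension. During these intervals Table 3's hold and stop rules cannot act on silent renal, hepatic or electrolyte toxicity unless someone orders an unscheduled test.

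The weight is modest. The weakness is confined to asymptomatic laboratory toxicity and the secondary toxicity objective, and the documents show little sign of such events. The gaps follow directly from the schedule; the mean delays rest on the uniform-onset assumption. The change should be made because it is cheap and removes most of the delay. Confidence is medium.

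**What to change.** Amend sections 1.7.2.3 and 7.3.1 and Table 1 together so that the biochemistry panel is taken once every 28-day cycle. Suggested wording for 7.3.1: *Obtain biochemistry panel once every 28-day cycle with the CBC.* Because the CBC is weekly in cycles 1 and 2, specify the draw at the cycle visit. The CBC schedule and Table 3's dose rules stay as written. The longest gap falls from 112 to 28 days.

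The cost is at most 9 extra routine panels per patient on draws already planned: 9 × 25 = 225 panels for 25 patients, or 9 × 14 = 126 if the trial stops at 14. If visits open the cycle and no day 1 panel is added, it is 8 per patient: 8 × 25 = 200, or 8 × 14 = 112. Early discontinuation lowers these figures. More mild abnormalities will be found and will need review.
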